9. STUDY TIMELINES*

Patient Subject Participant Involvement Timeline:

- ***Enrollment & Intake Visit: (Day 0)***
 - Informed consent
 - Non-biometric data – Contact information; Intake data points
 - Five-question Problem Areas in Diabetes (PAID-5) scale as well as the 17-question Diabetes Distress Scale (DDS) and supplemental questions will be administered
 - Device training (if randomized to CGM)

- Care coordination to DCOE (all patients)
- ***Outpatient Blood Sugar Monitoring (for intervention group only) (day 0-14)***
 - Continuous Glucose Monitoring – Sensor worn 24 hours a day for up to 14 days.
Data can be uploaded
- ***Follow Up: (~Day 14-21 post ED visit)***
 - Study team will meet patient at follow-up appointment
 - Biometric data – Downloaded
 - Non-biometric data – Five-question Problem Areas in Diabetes (PAID) scale as well as the 17-question Diabetes Distress Scale (DDS) and supplemental survey questions will be administered
 - Compensation (\$10)
- ***6 Months Follow up (no active patient involvement)***
 - Follow-up data points abstracted from electronic health record (EHR)

Provider Subject Participant Involvement Timeline:

- ***Follow Up: (~Day 14-21 post ED visit of patient subjects)***
 - Study team send survey questions to provider subjects immediately after they have a clinic encounter with a patient subject
 - This will be the only time point of participation for provider subjects

Study Timeline: We anticipate that recruitment will be complete by September 30, 2022. Primary data analysis will be complete by the end of March 2023.

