10. STUDY ENDPOINTS*

Our primary outcome The primary outcomes will be the rate of attendance at the follow-up visit and be the change in diabetes-related quality of life as measured by the PAID-5 scale and the DDS.

Secondary outcomes will include A1c levels, recurrent ED or EMS utilization, hospitalizations, and major cardiovascular events. We will also query DCOE providers regarding their satisfaction with the program, including a question about whether the CGM data are helpful for each patient.

Expectation: Our hypothesis is that CGM use after ED discharge will reduce the clinic no-show rate and decrease diabetes-related distress compared to the group with care coordination only.

There are no primary or secondary safety measures being recorded for the purposes of this study.

Safety measures will include number of device questions/concerns expressed by subjects during enrollment through their two-week follow up appointment, reported blood sugar events,

(high/low values), and return visits to clinic/ED/hospitalizations within the 2 week window of enrollment.

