- **Diabetes Center of Excellence Care Coordination:** Study Staff will follow up with ED provider to ensure that patients' have clinically indicated referral to diabetes center of excellence

→ **Appointment scheduling:** RA will make an appointment for the patient before ED discharge, if possible. If this is not possible, RA will contact the patient after discharge to arrange a follow-up appointment.

Outpatient Blood Sugar Monitoring: The CGM will be worn on the participants' upper arm continuously for 14 days (or until it falls off or the patient decides to remove it)

[figure not shown]
Visit #1 (~Day 14-21 Post-Discharge of patient subjects)

- **Documents:**
 - **Visit Data (RA facing)**
 - **Problem Areas in Diabetes (PAID-5) scale/Diabetes Distress Scale and supplemental questions**
 - **Fact sheet for provider subjects**
 - **Provider satisfaction survey**
- **CGM Data:** Biosensor data will be downloaded and reviewed
- **Material Collection:** Study Staff will collect CGM readers
- **Compensation:** Participants will be offered \$10 worth of gift cards to a retail store for completing visit #1.
- **Provider Survey:** immediately following an encounter with a patient subject, the provider taking care of each patient will be contacted by the study team as potential provider subjects. Potential provider subjects subsequently will be sent an email solicitation to participate in a Redcap survey. A fact sheet will be provided with that email. The survey will consist of 4 questions pertaining to their satisfaction with patient subject care coordination and/or their CGM utilization. Providers may be sent multiple surveys if they see multiple subjects who are enrolled in the study. This is the only involvement of the provider subjects.
- **No Shows:** *RAs will reach out to subjects who miss their follow-up appointment to (1) help them reschedule and (2) ask that they fill out the post-intervention questionnaire via an online link (or mailed paper copy or via phone, if desired)*

Follow up Data Collection (~6 months Post-Discharge)

- **Documents:**
 - **6 month follow up datasheet**
- **Data Collection:** The study team will query the EHR to collect follow up data points about enrolled subjects

Figure 1: Procedural Flow Sheet

t

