Sample Size: The primary outcomes are the clinic attendance rate and the change in diabetes-related distress, as measured by the Diabetes Distress Scale (DDS) and PAID-5 scale between the ED visit and the follow-up appointment date (19). Secondary outcomes include repeat ED/EMS utilization over 6 months, repeat hospitalizations, major cardiovascular events, and changes in hemoglobin A1c. For clinic attendance, we will aim to achieve attendance at 80% of the scheduled clinic visits. For a one-sided test at alpha=0.025 of a single proportion against a standard proportion (0.80), we will have 80% power to detect a difference of 0.13 (0.80 – 0.67) with a sample size of 83 subjects in the CGM group. Adjusted for 20% dropout, we will need approximately 100 subjects/group. For the DDS outcome, we will compare the change from baseline to the end of follow-up in the DDS between the two groups. Although we will fit the trajectory of the DDS change in each group using all DDS measures in a mixed effects model with repeated measures (MMRM), for simplicity in sample size estimation, we will calculate the sample size for an unadjusted comparison of the change between the two treatment groups. Based on a study of 267 subjects with diabetes (19), the standard deviation of the DDS was 1.0 across the three sites in that study. The DDS is a questionnaire of 17 questions, each scored on a Likert scale of 1 (not a serious problem) to 6 (serious problem), with the overall score calculated as the mean score across the 17 items. Thus, the range of the overall score is 1.0 – 6.0. With 100 subjects in each group, we can detect a difference of about 0.40 in the DDS change between the two groups. The literature on the DDS does not identify a clinically meaningful difference although Fisher, Polonsky, Hessler, Mullan (2012) suggest a difference of 0.5 as meaningful (20). Thus, our sample size will achieve power of greater than 80% to detect that difference.

Analysis Strategy: As indicated in the Sample Size section above, for the clinic attendance rate, we will conduct the initial unadjusted analyses using an exact test of the frequencies under the presumed population proportion (0.80) and the observed proportion. Adjusted analyses will be conducted using a logistic regression model for the proportion of clinic visits attended as the outcome in the intervention group with predictors including age, gender, time since diagnosis of diabetes, and other factors of interest.

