For the outcome of change in DDS, we will conduct the initial unadjusted analysis as described above in the Sample Size section. For adjusted analyses, we will include each DDS score in the longitudinal MMRM, so that we can model the trajectory of change as well as the individual changes over the period of follow-up. The time metric in this model will be the time (months) since study enrollment with predictors including age, gender, time since diagnosis of diabetes and other factors of interest. We will also investigate subgroups of interest using a Forest plot approach. We will plot the means and confidence intervals for the outcome for the two groups using Forest plots to display the total groups and subgroups of interest. We will also generate

longitudinal plots of A1c over time with the means and appropriate exact 95% confidence intervals at each time point. In addition, with the DDS trajectories available, we are able to use machine-learning approaches, such as growth mixture models, to identify clusters of patients with similar trajectories but who are not members of previously defined subgroups. Finally, we will conduct sensitivity analyses to determine if missingness of DDS scores are missing at random or missing not at random. For these analyses, we will use several methods, including the jump-to-reference imputation and the pattern mixture model approaches, to determine if the results using the sensitivity analyses are consistent with the MMRM results, indicating that the missingness is missing at random.

For the secondary outcomes, the change in HbgA1c will be modeled as for the DDS above. The other secondary outcomes can be modeled as binary outcomes and will be modeled as longitudinal logistic models.

Data Management Plan:

All study data will be recorded on a REDCap database established on a secure encrypted server on AWS. All access to the database will be through permissions established by the IT REDCap administrator. Investigators will have to log into the REDCap database to enter or view data. The REDCap database will be developed and implemented by the data management staff of the UMMS Quantitative Methods Core (QMC) with the direction of [name], QMC Director. Logic data checks will be built into the data entry process to help clean the data at entry. Quality control edits will be run to identify inconsistencies and questionable values in the data. The audit trail will be activated for the duration of the study.

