Contact Info - Contact information will be collected using the Redcap (Contact	- *Identifiable information	- Authorized Study Staff	- N/A	- Contact information will be transferred to the Master Code following

Info) and then transferred to the Master Code				completion of the enrollment and intake visit and the Redcap form will be destroyed
Intake Data Collection Sheet – RA Facing Collected using the Redcap form *Also see Section 12	Study ID# only	Authorized Study Staff	Directly entered by the RA into Recap	1) Destroyed upon completion of data collection verification 2) REDCap database will be archived once results have been published
Intake Data Collection Sheet- Patient Facing Collected using the Redcap form *Also see Section 12	Study ID# only	Authorized Study Staff	Directly entered by the participant into a secure online database using survey mode (REDCap)	1) Destroyed upon completion of data collection verification 2) REDCap database will be archived once results have been published
Info Sheet- Hyperglycemia	- N/A	- N/A	- N/A	- N/A
Info Sheet- Hypoglycemia	- N/A	- N/A	- N/A	- N/A
Info Sheet- CGM	- N/A	- N/A	- N/A	- N/A
Baseline Problem Areas in Diabetes (PAID) scale/ Baseline Diabetes Distress Scale and supplemental questions - Direct entry into REDCap	- Study ID# only	- Authorized Study Staff & Support Personnel	- Directly entered by the participant into a secure online database using survey mode (REDCap)	- REDCap database will be archived once results have been published
2 Week Follow up Data Collection Sheet 1) Collected using the paper form 2) Entered into REDCap *Also see Section 12	1) Study ID# only 2) Same as above	1) Authorized Study Staff 2) Authorized Study Staff & Support Personnel	1) Securely stored in the PI's locked office 2) Secure online database (REDCap)	1) Destroyed upon completion of data collection verification 2) REDCap database will be archived once results have been published
2 Week Problem Areas in Diabetes (PAID) scale/Diabetes Distress Scale and supplemental questions	- Study ID# only	- Authorized Study Staff & Support Personnel	- Directly entered by the participant into a secure online database using survey mode (REDCap)	- REDCap database will be archived once results have been published

- Direct entry into REDCap				
Provider subject email solicitation	-N/A	- Authorized Study Staff & Support Personnel	-N/A	-N/A

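### Agreement of the DDS sensitivity analyses with the MMRM cannot show that scores are missing at random, as Section 13 says it would

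*Combined protocol and SAP*

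**What the plan says.** Section 13 (Analysis Strategy) gives the aim: "we will conduct sensitivity analyses to determine if missingness of DDS scores are missing at random or missing not at random". The named methods are J2R imputation and pattern-mixture models, and their results will be compared with the MMRM "to determine if the results using the sensitivity analyses are consistent with the MMRM results, indicating that the missingness is missing at random". The aim and the conclusion make the same claim, and no other section qualifies it. The plan gives no delta, tipping point, identifying restriction or range of departures from MAR.

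Four further points in the same document bear on this:

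- DDS change is part of the primary outcome (Sections 10 and 13). The unadjusted comparison of change is the initial analysis; the MMRM is the adjusted one.
- The schedule has a baseline DDS and one later DDS at about day 14-21 (Sections 9 and 11). The data table in Section 26 lists only "2 Week Problem Areas in Diabetes (PAID) scale/Diabetes Distress Scale and supplemental questions" after baseline. The six-month step is chart abstraction.
- Section 10 expects that "CGM use after ED discharge will reduce the clinic no-show rate". For patients who miss the visit, Section 11 has staff "ask that they fill out the post-intervention questionnaire via an online link", or by mail or phone.
- No missing rate is given for DDS. The 20% dropout allowance in Section 13 belongs to the attendance calculation.

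**The concern.** MAR says that, given what was observed, the unseen scores follow the same distribution as the seen ones. MNAR says that they do not. The two differ only in data that are never collected, and this holds for any number of follow-up scores. J2R and pattern-mixture models each impose an assumption on the unseen scores. Comparing them with the MMRM shows how far the estimate moves under those assumptions, not which assumption is true.

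At stake is what may be said about a primary outcome. Under the stated rule, a report could present agreement as evidence for MAR when the MMRM is biased, or present ordinary J2R shrinkage as evidence against MAR when MAR holds.

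**Working it through.** The plan states no figure on this point. As context, its DDS detectable difference reproduces: for 0.40 with SD 1.0, two-sided 0.05 and 80% power (level and sidedness assumed), n = 99 per group against the 100 planned.

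**Inputs.** SD 1.0 is from Section 13 ("the standard deviation of the DDS was 1.0 across the three sites in that study"). Assumed: baseline to follow-up correlation r = 0.5; 20% of DDS missing per arm, borrowed from "Adjusted for 20% dropout, we will need approximately 100 subjects/group"; a true effect (CGM minus control) of -0.50; and logistic selection on the unseen follow-up score, with the slope given per DDS point. The MAR estimate regresses follow-up on baseline within each arm, which stands in for a two-time-point MMRM. J2R imputes missing CGM scores from the control-arm regression.

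**Step 1: algebra.** Let e be the MAR estimate, f the CGM-arm fraction missing, and delta the mean distance of unseen CGM scores from their MAR prediction, with control left at MAR. When missingness is unrelated to baseline:

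- J2R = (1 - f) x e, so the gap between the methods has size f x |e|.
- True effect = e + f x delta.

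Delta appears in neither estimate. With e = -0.50 and f = 0.20, J2R = 0.80 x -0.50 = -0.40. The same observed data fit a true effect of -0.50 - 0.20 = -0.70 (delta = -1) or -0.50 + 0.20 = -0.30 (delta = +1). The shift is in one arm only; equal shifts with equal missingness in both arms would cancel.

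**Step 2: large-sample simulation.**

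| Mechanism | True effect | MAR estimate | J2R |
|---|---|---|---|
| Completely at random, 20% | -0.50 | -0.50 | -0.40 |
| Equal MNAR in both arms, slope 1 | -0.50 | -0.50 | -0.40 |
| Equal MNAR in both arms | 0 | 0 | 0 |
| CGM-only MNAR, slope +1 | -0.50 | -0.63 | -0.50 |
| CGM-only MNAR, slope +2 | -0.50 | -0.71 | -0.56 |
| CGM-only MNAR, slope -1 | -0.50 | -0.37 | -0.30 |
| CGM-only MNAR, slope -2 | -0.50 | -0.29 | -0.24 |

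The rule fails both ways. In row 1 MAR holds and the methods differ; in row 3 MAR is false and they agree. For the -0.50 rows the ratio of J2R to the MAR estimate stays between 0.79 and 0.84, while the bias in the MAR estimate runs from none to 0.21.

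**Step 3: trial size** (100 per arm, 20% missing, 2,000 trials). The share of trials with J2R within 0.10 of the MAR estimate (an assumed threshold), MAR against equal MNAR with slope 1:

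- true effect 0: 99.5% against 99.9%
- true effect -0.25: 93.4% against 94.0%
- true effect -0.50: 52.3% against 53.8%

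Agreement follows the size of the effect and barely distinguishes these two mechanisms.

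**Step 4: when the MMRM is biased.** With equal slope 1 but 10% missing on CGM and 20% on control, the MAR estimate is -0.44, a bias of about 0.06. CGM-only slope 1 at 8% missing also gives about 0.06. Equal slope and equal 20% missing can still bias it if the variance differs by arm: a CGM residual SD of 1.1 against 0.866 on control gives -0.57, and 0.6 gives about -0.43.

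**Step 5: tipping points** (CGM arm only, 80 observed per arm), (|effect| - 1.96 x SE) / 0.20:

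- Unadjusted change, SD 1.0: SE = sqrt(2/80) = 0.158. Effect -0.50: (0.50 - 0.310)/0.20 = 0.95. Effect -0.40: (0.40 - 0.310)/0.20 = 0.45.
- ANCOVA, r = 0.5: SE = 0.866 x 0.158 = 0.137. Effect -0.50: (0.50 - 0.268)/0.20 = 1.16. Effect -0.40: (0.40 - 0.268)/0.20 = 0.66.

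**The case against.** The plan attaches no decision to the MAR verdict: no analysis or estimand changes with it. Checking whether suitable alternative methods agree with the MMRM is a proper robustness comparison, and the fault lies in the stated aim and one closing clause. This stands, and it limits the point to interpretation.

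The authors may have meant only that agreement is compatible with MAR. That does not rescue the clause, because agreement is just as compatible with MNAR (row 3 of the table).

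Mechanism can also move agreement. At a true effect of -0.50, CGM-only MNAR changes the within-0.10 share from 52.3% under MAR to 26.4% (slope +1) or 81.1% (slope -1). So it would be wrong to say that agreement never responds to mechanism. It does so through the bias in the estimated effect, and since the true effect is unknown, the mechanism cannot be read back from it.

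A missed visit is not a missing DDS, because questionnaires are sought from no-shows by other routes. This stands: the attendance hypothesis makes unequal missingness plausible but does not establish it.

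Finally, deleting two phrases cures the error. A tipping-point analysis is a preference, since the plan already allows several pattern-mixture approaches.

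**Conclusion.** The inference is wrong as written and should be corrected before analysis. Agreement depends on the size of the estimated effect and the fraction missing in the CGM arm. Mechanism enters only through any bias in that estimate.

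A reader might infer more than the documents support:

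- *That the DDS result will be biased, or that the main estimate is unsound.* The documents give no DDS missing rate and no evidence of MNAR. The MMRM can be biased when MNAR selection or outcome variance differs by arm, but every size above rests on assumed missing rates, r and slopes, and the 10% against 20% case gives only about 0.06. The MMRM is also the adjusted analysis, not the initial one.
- *That bias requires selection to differ by arm.* It does not; unequal variance is enough (Step 4).
- *That J2R or pattern-mixture models are the wrong choice.* They are suitable; only the conclusion drawn from them is at fault.

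No estimate changes. What changes is that a report on this primary outcome may not claim that MAR was shown.

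**What to change.** In Section 13, Analysis Strategy:

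1. Delete the aim of determining whether DDS missingness is MAR or MNAR, and the closing clause of the comparison sentence, from its comma on.
2. State MAR as an untestable assumption of the MMRM.
3. Report the J2R and pattern-mixture results as whether the conclusion is robust to the stated departures from MAR. Note that J2R shrinks a real effect by construction, so a gap from the MMRM is not evidence of MNAR.
4. Preferably, run the planned pattern-mixture analysis as a delta-adjusted tipping-point analysis, with delta varied by arm over a range fixed in advance, and say so if no tipping point lies within it. To help choose the range: at 100 per arm and 20% missing, the CGM-arm tipping point is about 0.95 to 1.2 DDS points for an effect of -0.50 and 0.45 to 0.7 for -0.40, depending on the standard error used.

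The cost is SAP wording and, for item 4, modest programming. No new data are needed.

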14. PROVISIONS TO MONITOR THE DATA TO ENSURE THE SAFETY OF SUBJECTS*

In accordance with **HRP-801 Prompt Reporting Requirements**, any unanticipated adverse events will be reported and the PIs will closely monitor all aspects of the study.

The PIs will be responsible for monitoring adverse events during the study. If an adverse event occurs, their role will be to identify the concern, to develop an appropriate response to alleviate or minimize any adverse event, and to ensure that the adverse event is reported in a timely manner to the appropriate authority. Participants will be monitored for the occurrence of any

undesirable experience or unanticipated benefit. Events may occur during recruitment, during home CGM use, and during the initial follow-up visit. We anticipate that these effects will be limited. We will assess whether an undesirable experience (adverse event) occurred and will record details of all adverse events on an adverse event case report form. We do not anticipate that any serious adverse events (death, life threatening illness, new serious or permanent disability) will occur. However, should such an event occur, we will report the event within 24 hours to the University of Massachusetts Medical School (UMMS) Institutional Review Board.

The adverse event case report form will include a description of all undesirable experiences, required interventions, and an assessment of the participant after the event if possible. An estimate of the extent of injury and prevention strategies will be reported. The principal investigators will classify the relationship of the study protocol to the event as follows:

- Not related: The event is clearly related to factors not related to the study protocol.
- Remote: The event was most likely related to factors not related to the study protocol.
- Possible: The event follows a reasonable temporal sequence associated with participating in the study and/or is consistent with events related to the study protocol but is possibly related to factors such as the participant's clinical state.
- Probable: The event follows a reasonable temporal sequence associated with participating in the study and/or is consistent with events related to the study protocol and cannot be reasonably explained by factors such as the participant's clinical state.

The severity of an adverse event in both groups is defined as a qualitative assessment of the degree or intensity of an adverse event as determined by the principal investigator as follows:

- Mild: No impact (in any way) on the participant.
- Moderate: Impacts on the participant but is not life-threatening or incapacitating.
- Severe: Fatal, life threatening, permanently disabling; severely incapacitating; requires/prolongs inpatient hospitalization.

All adverse events will simultaneously be reported to institutional officials. The report will summarize the facts of the case, including the date and a description of the participant; whether the event is related to the study's protocols; the steps that have been taken to address the issue; whether the event provides emerging knowledge about the risks of the study that should be conveyed to participants; and whether the consent form should be revised.

Due to the relatively low risk of adverse events with using a CGM, which are FDA-approved for people with both type 1 and type 2 diabetes, and the relatively short duration of the study, we do not plan on having a data safety monitoring board review.

The frequency of data review for this study is summarized in the following table:

Data Type:	Frequency of Review:
Participant recruitment (adherence to protocol on inclusion & exclusion criteria)	The PI will directly observe recruitment for the first five cases, then will observe random

	cases bi-monthly once the study is established.
Data collection methods	The PI will directly observe data collection on the first five cases, then will observe random cases bi-monthly once the study is established.
Integrity of data storage procedures	The PI will directly monitor data storage the first five cases, and then will review all data monthly once the study is established.

